UCSD Human Research Protections Program New Biomedical Application RESEARCH PLAN

Instructions for completing the Research Plan are available on the HRPP website. The headings on this set of instructions correspond to the headings of the Research Plan. General Instructions: Enter a response for all topic headings. Enter "Not Applicable" rather than leaving an item blank if the item does not apply to this project.

Version date: 9/30/2013

PROJECT TITLE 1.

A Double-Blind, Cross-Over, Placebo- Controlled Efficacy and Tolerability Study of oral cannabidiol (CBD) and tetrahydrocannabinol (THC) for Essential Tremor (ET)

2. **PRINCIPAL INVESTIGATOR**

[name].

3. **FACILITIES**

UCSD Altman Clinical Translational Research Institute [name]

ESTIMATED DURATION OF THE STUDY 4.

24 months

5. LAY LANGUAGE SUMMARY OR SYNOPSIS (no more than one paragraph)

Essential tremor (ET) is the most common neurological movement disorder, affecting up to 1% of the population and up to 5% of individuals over the age of 65. ET is characterized by often disabling tremors that occur when an individual moves. The tremors most commonly affect the hands, head, voice, and legs in order of frequency, leading to impairment in activities of daily living and morbidity. No pharmacological agent has been developed for ET, though existing agents such as propranolol and primidone are used off-label to reduce tremor amplitude. Deep brain stimulation surgery is often reserved for only individuals with the most severe tremors. Patients with ET have long reported tremor benefits with the use of cannabis, though no controlled trials have been conducted. We plan to conduct the first double-blind, placebo-control clinical trial of cannabis in an oral capsule. We will use various validated tremor rating methods to quantify tremor severity, while looking at tolerability and safety.

6. SPECIFIC AIMS

The present study seeks to assess the efficacy and tolerability of TILRAY TN-CT120LM (FDA IND#137400), a pharmaceutical-grade formulation containing THC and CBD, vs. placebo in an Essential Tremor patient population. The study is intended to collect pilot data to determine whether larger studies are warranted and assist in their future design.

Aim 1: To determine if short-term exposure to orally administered THC/CBD improves tremor amplitude in ET patients. Hypothesis 1: ET patients receiving THC/CBD orally will have reduced peak tremor power (compared with their own baseline measures) by accelerometry and spirography vs. placebo.

Aim 2: To determine acute and short-term tolerability of orally administered THC/CBD. Hypothesis 2: ET patients receiving THC/CBD orally will be associated with more frequent ratings of sedation on the Common Toxicity Criteria compared with placebo.

Aim 3: To characterize the relationship between THC/CBD exposure with clinical response (i.e. tremor amplitude) to define a plausibly useful dose range for evaluation in future confirmatory clinical trials.

BACKGROUND AND SIGNIFICANCE 7.

7.1 There is a great medical need for a more effective treatment for essential tremor.

Essential tremor (ET) is traditionally defined as bilateral, generally symmetric postural and kinetic tremor of the upper extremities that is not attributable to identifiable causes, and has been present for at least 5 years. A meta-analysis of prevalence studies indicates that 0.4 to 0.9% of the general population has ET. The figure rises to 4.6 to 6.3% among those 65 years or older (Louis and Ferreira, 2010). ET is a common cause of embarrassment, social withdrawal, disability, and loss of occupation.

The most commonly utilized medications for ET are propranolol, primidone, topiramate, gabapentin, and benzodiazepines. Unfortunately, the long-term efficacy and tolerability of current medications leave much to be desired. If one surveys hundreds of ET patients, it is found that one-third have stopped all ET medications, even those with the most severe tremor. In other words, many of the most disabled ET patients have abandoned the search for a drug that can help them. Over half the patients who try primidone, propranolol, diazepam or topiramate end up stopping them, and the percentage is higher with other anti-ET medications (Louis et al., 2010).

This situation arises from lack of knowledge about the cause of ET, so that clinical trials on medications have been performed on the basis of guess-work or serendipity, with the majority ending with a negative result. The lack of any new positive recommendations by the 2011 Academy of Neurology evidence-based guideline update on the treatment of ET attests to the poor yield of present approaches to drug discovery (Zesiewicz et al., 2011).

The lack of knowledge about the etiology of ET is clearly a barrier to drug discovery. However drug discovery has proceeded for other neurological conditions in which the precise etiology is not clear, such as epilepsy, migraine and multiple sclerosis. We suspect that another barrier to drug discovery for tremor is the underappreciation by pharmaceuticals of the social, economic, and clinical significance of ET. Given that half of ET persons aged 65 and over take medication for tremor (Louis et al., 2000), and 2012 demographic data that, among the 1,006.9 million persons living in the European Union, the United States, Japan, Canada, Australia and New Zealand, 163.7 million persons are aged 65 years and over, it can be estimated that 3.8 million persons in this age group in these countries are seeking or receiving medication for ET. If they are willing to pay \$4 a day to treat their tremor, the market size would be \$5.5 billion per year. Given that persons under age 65 are not included in this calculation, and another 2-3 billion persons in Asia, Latin America, Africa and the Middle East have joined or will soon join the middle class, the market size is likely much greater, at \$10-15 billion per year world-wide. Any new ET medication that is highly effective and well tolerated will likely soon dominate a large market.

In addition to neurologists empirically identifying potential treatments for tremor, ET patients themselves have empirically sought remedies. Numerous patients have identified low-dose alcohol as more effective than any prescribed ET medication for tremor suppression. Of particular interest, many ET patients have identified marijuana as more effective and well-tolerated for tremor than any prescribed ET medication, as discussed in the next section.

7.3 What is the mechanism by which cannabinoids may suppress tremor?

Although the cause of ET is unknown, we do have some knowledge about the neural circuits that may be involved in tremor initiation and expression. It is therefore appropriate to consider these circuits and how cannabinoids may affect them.

ET tremor does not disappear with anesthesia of the limb, or the frequency change with mechanical loading, indicating that it arises from a central generator. Magnetoencephalography during tremor in ET subjects reveals an oscillatory network involving the cerebellum, thalamus, motor cortex, and brainstem (Schnitzler et al., 2009). In ET, PET scans show increased blood flow in the cerebellum even at rest (Boecker et al., 1996). ET patients have many anomalies of cerebellar function, including imbalance, irregular finger tapping, and subtle eye movement abnormalities, some of which improve with successful tremor treatment. The highly effective deep brain stimulation therapy acts by blocking outflow from the cerebellum to the motor thalamus. Transcranial magnetic stimulation of the cerebellum improves tremor (Popa et al., 2013). Our concept of the circuits involved in excessive cerebellar oscillatory activity underlying action tremor is displayed in Figure 3. A key concept is that these circuits form feedback loops, so that disease processes could occur at one or more of several sites within the loops to unleash and sustain the abnormal oscillations.

Likewise, interventions that dampen the oscillation could be applied at one or more points within these loops, and need not coincide with the site of disease.

In considering the role of various components of the cerebellar system in tremor, we consider a ventral tier, likely involved in oscillation initiation, and a dorsal tier, involved in oscillation amplification.

Inferior olive (IO) PET scans of ET patients have shown increased IO glucose utilization, and increased IO blood flow when patients are given alcohol (Boecker et al., 1996). Eyeblink conditioning, which depends on the olivo-deep cerebellar nuclei (DCN) projection, is impaired in ET patients, but improves after thalamic DBS. The IO is a natural pacemaker, and offers a mechanism for providing rhythmicity to cerebellar oscillatory activity.

Deep cerebellar nuclei (DCN) The excitatory DCN neurons are the sole output neurons of the cerebellum, and in ET tremor an oscillatory loop involves DCN-motor thalamus-motor cortex-IO/pons-cerebellum. It is thus not surprising that strokes that severely damage the DCN, motor thalamus, frontal white matter or internal capsule can eliminate tremor in ET patients (Dupuis et al., 2010). The participation of DCN in tremor is demonstrated by PET imaging in ET and by c-fos imaging in rodents given the tremorigenic drug harmaline. Interestingly, partial lesions of the DCN produce action tremor in patients with head trauma and tremor in rats after chemical DCN lesions. An extensive literature has documented that action tremor ensues after lesions of DCN in monkeys (Gemba et al. 1980). Thus the DCN may be involved in both the initiation and propagation of the oscillations that underlie tremor.

Cerebellar cortex *Pcd* mice that lose all Purkinje neurons still respond to harmaline with tremor, but the tremor is of lower amplitude and frequency compared to wild-type, indicating that Purkinje cells have a role in amplifying tremor. PET scans in ET patients demonstrate increased blood flow in the cerebellar cortex, present at rest, and increased with tremor. This increase is abolished by alcohol (Boecker et all, 1996). In the harmaline model, granule cells express c-fos early. Strokes involving the pons, which interrupt mossy fiber projections to granule cells, abolish tremor in ET (Dupuis et al., 2010). In summary, the components of the cerebellar cortex appear to be important for the amplification of hyperoscillations that underlie action tremor.

How might cannabinoids affect tremor in ET? Endocannabinoids are released by post-synaptic neurons to act retrogradely on pre-synaptic cannabinoid receptors to modulate the release of excitatory and inhibitory

neurotransmitters. The CB1R is intensely expressed on the terminals of parallel fibers derived from granule cells that contact Purkinje cells. CB1Rs are also expressed on terminals of basket and stellate interneurons, and on climbing fibers, all projecting to Purkinje cells. The Purkinje cells themselves do not express CB1Rs. Aside from the rubro-olivary projection to inferior olive, there is little CB1R expression in the DCN or inferior olive. CB2Rs are also expressed in the terminals of parallel fibers and

Figure 3. Schematic of neural circuits involved by hyperoscillatory activity in action tremor. See text for discussion. Arrowheads connote excitation and bar endings connote inhibition. A

reciprocal loop involving stellate and Purkinie cells is omitted. CF: Climbing Fibers; DCN: Deep Cerebellar Nuclei; Go: Golgi interneurons; Gr: Granule cells: IO: Inferior Olive; MF: Mossy Fibers

basket cells, but are also intensely expressed in the mossy

fibers to the granule cell layer, neuropil of DCN, and in spinal cord terminals within the inferior olive (Suarez et al. 2008). Given this strong expression of cannabinoid receptors within all the components of the cerebellar system that have been implicated in tremor initiation and expression, it can be seen that endogenous or exogenous cannabinoids could be expected to influence the hyperoscillations that underlie tremor.

An alternative mechanism could be the activation of glycine receptors. Glycine receptors are pentamers made of alpha and beta subunits. There are 4 isoforms of alpha, and one of beta. Δ^9 -Tetrahydrocannabinol (THC) and cannabidiol (CBD) (see Figure 4) act as positive allosteric modulators of glycine receptors, including alpha1, alpha2 and alpha3 receptors (Ahrens et al., 2009; Hejazi et al., 2006). It has been suggested, for example, that CBD and related compounds exert analgesic effects against chronic pain via spinal alpha-3 glycine receptors, as these compounds suppress pain in CB1 knockout mice, but not in alpha3 glycine receptor knockout mice (Xiong et al., 2012). In the cerebellum, Purkinje cells and deep cerebellar nucleus neurons strongly express messenger RNA for glycine receptors (Fujita et al., 1991). The deep cerebellar nuclei,

Cannabidiol (CBD)

Figure 4. Chemical structures of THC and CBD

from which all cerebellar outlow emanates, including tremor-associated oscillations, are composed of three types of neurons: (1) large, glutamatergic output neurons, (2) GABAergic neurons that project to the inferior olive, and (3) glycinergic or mixed glycinergic/GABAergic interneurons. All three types receive Purkinje afferents. The glycinergic interneurons project to the large DCN output neurons, and thus are positioned to play an important role in cerebellar output (Pedroarena and Kamphausen, 2007).

These glycine receptors, composed of alpha1 and beta subunits, might be allosterically potentiated by cannabinoids, thereby suppressing tremor.

7.4 Objective assessment of efficacy can be performed with a relatively small number of ET subjects Tremor is reliably elicited during posture and movement in persons with ET, thus permitting assessment of efficacy with relatively few subjects compared to other medical or neurological conditions that are characterized by intermittent events. Cross-over Phase 2 trials for ET that use rating scales typically employ 20 to 60 subjects. Moreover, the use of digital spirography and accelerometry provide greater power at smaller sample sizes, as these measures appear to be more sensitive and reliable than the use of rating scales. In the ET field, the standard is to include placebo in the first reported trial of a treatment. The reason for this is that in the 1980's and 1990's numerous open-label positive results could not be replicated in controlled trials. Given the paucity of new treatments for ET in the past 10 years, knowledge of a positive result with even a small trial will rapidly become disseminated within the ET community. It may be noted that none of the medications currently prescribed for ET are FDA-approved for that condition. A single positive Phase 2 study can result in a marketed drug gaining access to the \$5-15 billion global ET market.

8. PROGRESS REPORT

Based on preliminary date from the first 5 subjects enrolled, we have learned a number of things to date that are being integrated into this protocol amendment:

- The dosing maximum that we have selected was poorly tolerated at 3 capsules administered concurrently, while it was tolerated by some subjects at the 2-capsule dose. We are modifying the protocol to limit the maximum concurrent administration of study drug to 2 capsules QAM and providing the last capsule in the evening.
- The only adverse effect to date took place when a subject did not take the study drug after a meal. This is already specified in both the protocol and consent, and we are simply emphasizing this and providing regular reminds to subjects.
- The frequent monitoring of vital signs, efficacy measures, and adverse effects within the first 3 hours of each study visit are excessive since the onset of effect in all subjects has been 2-3 hours post-dose. We are modifying the protocol to reduce the number of initial assessments and extending the duration of each study visit to 4 hours to allow for an enhanced sensitivity in identifying adverse effects and efficacy.

9. RESEARCH DESIGN AND METHODS

9.1 Rationale for Study Design Selection

The overall goal of this pilot trial is to determine whether TILRAY TN-CT120LM (FDA IND#137400), a pharmaceutical-grade formulation containing THC and CBD, is a viable therapeutic option for the management of ET. The primary endpoints will include safety and efficacy. Since the therapeutic dose of THC/CBD to manage ET is unknown, the study is designed to include a titration of the investigational drug to determine therapeutic doses. The protocol allows for a maximum dose of 15mg of THC and 300mg of CBD.

9.2 Strategies/Procedures for recruitment

Subjects with a diagnosis of ET will be recruited from the UCSD Movement Disorder Center and the general community. There will be an emphasis on obtaining a diverse sample composed of equal numbers of males and females, as well as an equal number of subjects above and below the age of 50.

9.3 Description of Screening and Study Design

SCREENING VISIT

After being screened for inclusion/exclusion criteria and providing informed consent, subjects will undergo a complete neurological examination to confirm their diagnosis of ET and exclude other neurological disorders. Additional measures collected during this visit are listed in Appendix 1. Note that subjects will need to have been on a stable dose of their medications for a minimum of 6 weeks prior to the screening visit and will be

encouraged to remain on these doses for the remainder of the study period. Subjects will be asked about their other tremor medication doses at each follow-up visit to confirm stable doses.

VIDEOTAPED TETRAS

As part of each study visit (1-3), subjects will complete a TETRAS rating scale while being videotaped. This is intended for rating purposes by two blinded raters at the completion of the study.

RANDOMIZATION

After completion of the screening visit, subjects will be assigned to one of two possible treatment arms based on a pre-set randomization matrix. Only the research pharmacy who will be responsible for dispensing the doses will be aware of which of two treatment options will be provided, but not the identity of the particular agent. The equivalence of the THC/CBD and Placebo will be equally matched by the manufacturer, making it difficult for the subject to discriminate which arm they are on. Subjects will be asked which arm they are receiving at each assessment visit and on telephone follow up to assess for potential unblinding.

DOSE TITRATION AND TREATMENT

On visit 1 and 5, subjects will receive 1 capsule of IMP every morning. On visit 2 and/or 6, if the subject tolerated 1 capsule then they would receive 2 capsules every morning. Alternatively, if 1 capsule was not tolerated, the timing of the administration would be changed to 1 capsule in the evening. At visit 3 and/or 7, if the single nightly capsule was not tolerated, the subject would be dropped at this visit. If the 2 capsules every morning were tolerated, the subject would then receive 2 capsules in the morning and 1 capsule in the evening. If 2 capsules in the morning were not tolerated, the subject dosing would be changed to 1 capsule in the morning and 1 capsule in the morning and 1 capsule nightly. Subjects will remain on the highest tolerable dose for the duration of the period until visit 4 or 8 (See Appendix 2).

The starting dose, titration schedule and target dose were selected based on safety, tolerability and efficacy data reported in previous studies using cannabinoids to treat pain (Langford et al., 2013; Portenoy et al., 2012; Johnson et al., 2010). Adverse effects will be inventoried at each study visit. If the patient or investigator feel that the higher study drug dose is causing troublesome side effects, the dosage may be lowered. Food intake can affect systemic exposure of cannabinoids (Zgair et al. 2016). Subjects will be advised to schedule their dose at a similar time every morning after breakfast to maintain similar systemic exposure throughout the study. Regular reminders will be provided to subjects to ensure they are taking the study drug post-meals. During study visits when drug is administered, subjects will be provided with a standardized FDA high-fat, high-calorie meal prior to taking the study drug.

DOSE TAPER AND WASHOUT

After completing a 2-week course on 15/300 mg/day of THC/CBD or placebo, subjects will return on this dose for assessment and completion of the various measures detailed in Appendix 1. After completion of this visit, subjects will taper from the treatment gradually over 1-week, in similar fashion to the dose titration up to the target dose. Subjects will then complete a 3-week washout period prior to being crossed-over to the alternate arm. This is to allow subjects to return to their baselines. The duration selected is conservative and takes into consideration the known elimination half-life of THC/CBD.

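### Section 9.3: as printed, the Visit 3/7 regimen for subjects who did not tolerate 2 morning capsules equals the regimen for those who did (15/300 mg/day); very probably a drafting slip for 10/200 mg/day

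*Combined protocol and SAP*

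**What the plan says.** Section 9.3 (Dose Titration and Treatment) starts each period with 1 capsule every morning. At Visit 2/6, a subject who tolerated this goes to 2 morning capsules; one who did not moves the single capsule to the evening. At Visit 3/7, if 2 morning capsules were tolerated, "the subject would then receive 2 capsules in the morning and 1 capsule in the evening". If they were not, dosing "would be changed to 1 capsule in the morning and 1 capsule in the morning and 1 capsule nightly".

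Three other statements bear on how this is read:

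- The same paragraph continues: "Subjects will remain on the highest tolerable dose for the duration of the period until visit 4 or 8", and refers to Appendix 2.
- Later in 9.3, if the patient or investigator judges that the higher dose "is causing troublesome side effects, the dosage may be lowered".
- The Dose Taper and Washout paragraph describes the assessment visit as taking place "After completing a 2-week course on 15/300 mg/day of THC/CBD or placebo".

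The Progress Report (section 8) gives the background. Three capsules taken together were poorly tolerated among the first 5 subjects, and the study drug was "tolerated by some subjects at the 2-capsule dose". The amendment therefore aims to "limit the maximum concurrent administration of study drug to 2 capsules QAM", with the last capsule given in the evening.

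**The concern.** The two branches of a tolerance rule should lead to different doses. As printed they do not: a subject who has just failed on 2 morning capsules keeps those 2 and gains a third at night. Staff working from the text of 9.3 alone could take the wrong regimen from it, and do so blinded to treatment. The statements about a tolerable dose and about lowering the dose show the direction to take, but neither names a replacement regimen.

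At stake are the safety and tolerability of the subjects who reach this branch and, secondarily, a clear record of the dose assigned, since Aim 3 seeks a useful dose range for later trials.

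**Working it through.** **Inputs**

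- Capsule strength: 5 mg THC and 100 mg CBD (Appendix 2, note).
- Maximum dose: 15 mg THC and 300 mg CBD (section 9.1).
- Visit 3/7 rules: section 9.3.
- Planned visit days: 1, 3, 6 and 22 in Period 1; 50, 52, 55 and 71 in Period 2; window ±3 days (Appendix 1).

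**Formula.** Daily dose = (morning capsules + evening capsules) × (5 mg THC, 100 mg CBD).

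**The plan's own figure.** The tolerated branch is 2 + 1 = 3 capsules: 3 × 5 = 15 mg THC and 3 × 100 = 300 mg CBD. This reproduces the stated maximum.

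**The not-tolerated branch**

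| Reading | Morning | Night | Capsules | THC/CBD, mg/day |
|---|---|---|---|---|
| As printed (1 + 1 morning, 1 night) | 2 | 1 | 3 | 15/300 |
| Repeated phrase removed | 1 | 1 | 2 | 10/200 |

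The dose that was not tolerated is 2 morning capsules, 2 × (5, 100) = 10/200 mg/day. Read literally, the rule raises the daily total by one capsule, 15/10 = 1.5 times the dose just failed. With the phrase removed, the total stays at 10/200 mg/day and is split between morning and night.

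**Which reading is intended.** At Visit 2/6, intolerance of 1 morning capsule keeps the total at 1 capsule and moves it to the evening. The corrected Visit 3/7 rule follows the same pattern: same total, less in the morning. The literal reading breaks that pattern and makes the two branches identical, so the rule would have no purpose.

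**Taper paragraph.** Section 9.3 allows a subject to finish a period on 1 evening capsule (5/100 mg/day) or, once corrected, on 1 + 1 (10/200 mg/day). The taper wording covers only 15/300 mg/day.

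**Visit window.** The planned titration steps are 3 − 1 = 2 and 6 − 3 = 3 days in Period 1, and 52 − 50 = 2 and 55 − 52 = 3 days in Period 2. A ±3-day window is longer than the first step and equal to the second. The later intervals are planned at 22 − 6 = 16 days (71 − 55 = 16 in Period 2) on the final dose, and 50 − 22 = 28 days between Visits 4 and 5. Section 9.3 separately states a 2-week course, and a 1-week taper plus a 3-week washout (7 + 21 = 28 days).

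**The case against.** The strongest reply is that nobody would follow the sentence literally. It contradicts its own purpose, its last two elements already spell out the intended regimen, and the next sentence calls for the highest tolerable dose. Appendix 2, to which the paragraph refers, is the titration plan itself; its diagram is not visible in the text reviewed and may be correct. All of this stands, and it is why the point is minor. It does not remove the point: a correct diagram would leave the diagram and the text in conflict within one protocol.

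A reader might infer stronger conclusions that the documents do not support.

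- *That subjects are likely to be harmed.* Even read literally, the morning dose stays within the 2-capsule cap and the extra capsule is taken at night. The Progress Report does not say how many of the first 5 subjects failed on 2 capsules, and it states: "The only adverse effect to date took place when a subject did not take the study drug after a meal".
- *That the ±3-day window is an error allowing escalation with no minimum time on a dose.* The readable text gives no minimum for the titration steps, but Appendix 2 may. Escalation depends on tolerance. Onset so far was 2 to 3 hours after dosing, visits are being extended to 4 hours, and vital signs, PRO-CTCAE and EKG are scheduled at each titration visit. For the later intervals, combining opposite ends of the windows gives 16 − 6 = 10 days on the final dose, or 28 − 6 = 22 days between Visits 4 and 5. That lets a table heading override the durations stated in 9.3. Read together, those durations limit the window.
- *That the taper wording requires every subject to reach 15/300 mg/day.* It describes the target-dose course; the titration paragraph plainly allows less.

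**Conclusion.** The dosing sentence is wrong as written. It assigns 15/300 mg/day where 10/200 mg/day is evidently meant, a difference of one capsule (5 mg THC, 100 mg CBD) a day, and it makes the two Visit 3/7 branches identical. This is very probably a drafting slip, and the dose-lowering provision and the tolerable-dose rule reduce its consequences. It is minor, but worth correcting because it is an instruction that staff act on.

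The conclusion about the printed text needs only the wording of 9.3 and the capsule strength. The intended dose is an inference from the parallel Visit 2/6 rule and should be confirmed against Appendix 2. The taper wording is a consistency edit. The visit window is at most a scheduling suggestion. Neither the sample size nor the primary analysis method is affected.

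**What to change.** 1. Check the Appendix 2 diagram. If it shows 1 morning and 1 nightly capsule, correct the text to match, for example: 'If the 2-capsule morning dose was not tolerated, dosing changes to 1 capsule each morning and 1 each night (10/200 mg/day).' If it shows anything else, the investigator should decide which regimen is meant and make both places agree.
2. In the taper paragraph, replace the fixed 15/300 mg/day with 'the highest tolerated dose (up to 15/300 mg/day)'.
3. Optional: state that titration visits stay in order, and count each from the actual date of the previous visit. This costs some scheduling flexibility and is a matter of preference.

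Items 1 and 2 need a short amendment changing one sentence and one phrase, with no effect on visits, sample size or analysis. Until it is approved, a clarification to the staff who titrate and dispense would help.

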APPENDIX 1: STUDY OVERVIEW

EVENT	VISIT 0: SCREENING	VISIT 1: DOSE TITRATION	VISIT 2: PK	VISIT 3: PK	TREATMENT PHASE	VISIT 4: ASSESSMENT	TAPER	WASHOUT	VISIT 5: DOSE TITRATION	VISIT 6: PK	VISIT 7: PK	TREATMENT PHASE	VISIT 8: ASSESSMENT	TAPER	TELEPHONE FOLLOW-UP	TOTAL DAYS
TOTAL DAYS	0	ų	5	1	16	1	5	22	ų	5	1	16	1	5	1	77
DAY NUMBER (±3)	0	1	3	6		22	23	28	50	52	55		71	72	77	
Consent	х															
Neurological Exam	х					x							х			
Vital Signs	х	х	Х	x		х			х	х	x		х			
TETRAS (video)	х					х							х			
Spirography	Х					X							Х			
Accelerometry	Х					Х							Х			
CGI/PGI						Х							Х			
PRO-CTCAE	х	x	х	x		х			x	х	x		х		х	
C-SSRS	Х					Х							Х		Х	
Lab Testing - pregnancy, CBC, CMP, Drug screen	x					x							x			
EKG*	x	x	x	x		x			x	x	x		x			
PK Sample(s)			Х	x		X				x	х		х			

* EKG at screening, then post-dose at each subsequent visit.

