9.16.3 APPENDIX 3: PHARMACOKINETIC SAMPLING TIMES**

DAY #	TIME
3	Trough
6	Trough
22	Trough + Pseudorandom (1,2,3,
	or 4 hrs/post-dose) sample

**NOTE: Samples will be collected for drug and placebo to maintain blinding, but PK lab will be unblinded in order to process only drug samples. If subject receive placebo first, PK days will be: #52, 55, and 71.

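### Visit doses follow a high-fat meal and home doses a meal of unspecified content, so feeding state is largely confounded with PK sample type and the Aim 3 dose range could be mis-scaled in either direction

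*Combined protocol and SAP*

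**What the plan says.** Section 9.3 (Dose Titration and Treatment) gives the premise: "Food intake can affect systemic exposure of cannabinoids". For home dosing it adds: "Subjects will be advised to schedule their dose at a similar time every morning after breakfast to maintain similar systemic exposure throughout the study", and "Regular reminders will be provided to subjects to ensure they are taking the study drug post-meals". Neither sentence specifies what the meal contains. For clinic dosing it is specific: at visits with dosing, "subjects will be provided with a standardized FDA high-fat, high-calorie meal prior to taking the study drug".

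Appendix 3 schedules trough samples only on days 3 and 6. The day 22 entry begins "Trough + Pseudorandom (1,2,3" and continues to 4 hours after the dose. When placebo comes first, the PK days are 52, 55 and 71.

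Appendix 1 places spirography, accelerometry and video TETRAS at screening, Visit 4 and Visit 8. Its footnote, "EKG at screening, then post-dose at each subsequent visit", implies dosing at every visit after screening.

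Section 9.4 (Pharmacokinetic Analyses) names age, sex, body size and race as factors to be related to exposure, and uses the final population model for Monte Carlo simulation across oral doses. Under Aim 3 (section 6), the exposure-response work is to "define a plausibly useful dose range for evaluation in future confirmatory clinical trials".

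**The concern.** The plan sets out to hold exposure steady and then specifies two feeding conditions, one fixed and one open. That would matter little if PK samples were spread across both conditions, but they are not. Absorption is observed only after the visit meal, and troughs mainly reflect home meals. A difference in bioavailability between the two states would look much like a feature of the absorption and elimination profile. No feeding-state term is named in the PK plan, and no record of home meals or dose times is described.

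What is at stake is the translation from concentration to dose. If participants in a later trial dose as these participants do at home (an assumption), a model that mixes the two states without knowing it may project the wrong dose for a given target concentration.

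**Working it through.** The plan gives no food-effect figure, so there is nothing of its own to reproduce. The check has three parts.

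**1. How many doses follow the visit meal.** Inputs are the full titration in section 9.3 (1 capsule each morning on days 1–2, 2 each morning from day 3, plus 1 each evening from day 6) and the nominal visit days in Appendix 1 (1, 3, 6, 22). The count runs to the day 22 morning dose.

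- Morning doses: 4 of 22 = 18%.
- Dosing occasions: 22 mornings + 16 evenings (days 6–21) = 38; 4 of 38 = 11%.
- Capsules: 2×1 + 20×2 + 16×1 = 58; at visits 1 + 2 + 2 + 2 = 7; 7 of 58 = 12%.

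**2. Which state each PK sample reflects.**

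| Sample | Last dose before it | Feeding state of that dose |
|---|---|---|
| Day 3 trough | Day 2 morning | Home |
| Day 6 trough | Day 5 morning | Home |
| Day 22 trough | Day 21 evening | Home |
| Day 22, one of 1–4 h post-dose | Day 22 at clinic | Visit meal |

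The confounding is not complete. Only two doses precede the day 3 trough, and the first is the day 1 clinic dose. Ignoring absorption, and with an assumed 24 h half-life, that dose supplies 0.25/(0.25 + 0.50) = one third of the trough. With a 4 h half-life it supplies 2⁻¹²/(2⁻¹² + 2⁻⁶), about 1.5%.

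**3. How large the error could be (illustration only).** Every kinetic input is an assumption: one compartment, absorption rate 0.7/h, half-life 4 to 48 h, evening dose 12 h after the morning dose. R is the visit/home bioavailability ratio. With a_i capsules at dose i and s_i hours since that dose,

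C(t) = Σ a_i · F · R_i · ka/(ka − ke) · (exp(−ke·s_i) − exp(−ka·s_i)), where R_i = R at visits and 1 at home.

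Error-free concentrations were generated for 16 subjects at the Appendix 3 times, with the post-dose sample spread evenly over 1, 2, 3 and 4 h. A model with a single F and a single ke, blind to feeding state, was fitted by least squares on the log scale with ka held at 0.7/h. The table gives predicted/true home concentration 2.5 h after the day 22 dose.

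| Half-life | R = 0.5 | R = 1 | R = 2 | R = 4 |
|---|---|---|---|---|
| 4 h | 0.61 | 1.00 | 1.68 | 2.84 |
| 12 h | 0.72 | 1.00 | 1.46 | 2.24 |
| 24 h | 0.88 | 1.00 | 1.32 | 1.84 |
| 48 h | 0.94 | 1.00 | 1.19 | 1.63 |

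Under linear kinetics, an over-prediction by a factor k makes the dose projected for a target concentration 1/k of the one needed. At R = 2 that is 1/1.19 = 0.84 down to 1/1.68 = 0.60; at R = 4, 0.61 down to 0.35. At R = 0.5 it runs the other way, 1/0.94 = 1.06 up to 1/0.61 = 1.64.

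**The case against.** Every dose is meant to be taken fed, and fixing the meal on measurement days reduces variation between subjects. Both periods use the same visit meal, so the drug-placebo contrast is balanced. Concentration and tremor are measured at the same visit, so their direct pairing is not biased by the meal. Three of the four PK samples per subject are mainly home-fed troughs, which dilutes any error. Appendix 1 is only an overview: it also omits the medication check and the arm-guess question that section 9.3 requires. Section 9.4 does not say its list of factors is exhaustive. The dosing plan in Appendix 2 cannot be read in the available text. Aim 3 asks a pilot only for a plausible range.

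Most of this stands and limits the point. A reader might infer that the dose range will come out too low, that it will be wrong by the full food-effect ratio, or that the simulations describe high-fat dosing alone. The documents support none of these. They give no direction of effect and no home-meal content, and in every case calculated the error was smaller than the assumed food effect. It would also be too strong to say that a food effect cannot be separated at all, given the clinic dose's contribution to the day 3 trough.

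The objection does not remove the conversion from concentration to dose. Section 9.4 also anticipates an effect-compartment model driven by the plasma profile over time, so a mis-described absorption phase could enter the exposure-response model by that route.

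**Conclusion.** The point holds in limited form, as a minor matter with a cheap improvement available. Two feeding conditions sit beside a stated aim of similar exposure, and the sampling plan largely aligns them with sample type. If they differ in bioavailability, the Aim 3 dose range can be mis-scaled either way. If they act alike, there is no error. The illustrative errors of about 1.2–1.7 times (R = 2), 1.6–2.8 times (R = 4) and 0.6–0.9 times (R = 0.5) rest wholly on assumed ratios and kinetics and are not estimates for this product.

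Two statements depend on inference. Dosing before the Visit 4/8 tremor tests is suggested by the EKG footnote and by the 4-hour visit described in section 8, but the order of tests and dose is not stated. That Visit 4/8 is the only on-drug tremor visit follows Appendix 1. Section 9.3 instead puts TETRAS at visits 1–3, though those are visit-meal days too.

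A reader might extend the point to the primary spirography comparison. The documents do not support that, because the visit meal is the same in both periods.

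**What to change.** Reconcile the two feeding instructions in section 9.3 with the stated aim of similar exposure, or state that the difference is intended. This review does not choose a meal or a dose.

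If the difference remains:

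1. Record the time, capsule count and meal type of the last doses, morning and evening, before each PK sample. This should start before further samples are taken, because a home meal that was not recorded cannot be reliably recovered later.
2. Run the Monte Carlo dose simulations over a stated range of relative bioavailability between the two feeding states, on both sides of 1. A sensitivity range is preferable to relying on a fitted covariate, since one post-dose sample per subject, always in the same feeding state, can hardly estimate that effect.
3. State that the Aim 3 dose range is conditional on the feeding state assumed.

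The cost is a short form entry, one sensitivity run and a narrower Aim 3 claim. If the instructions are instead reconciled by changing the visit meal, some standardisation between subjects may be lost, and items 2 and 3 would need rewording to match.
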